Assure repeatable marking of treatment area at each treatment visit

STUDY DESIGN OVERVIEW

This study is a prospective, baseline controlled, multi-center, one arm clinical study showing the performance and safety of the UltraShape Power treatment for abdominal non-invasive fat and circumference reduction.

Up to 120 Healthy subjects in up to 10 investigational sites will be enrolled in this study. All subjects will undergo an assessment of their general health. During the treatment period, subject’s fat thickness and circumference will be measured and three successive bi-weekly (two weeks interval) treatments will be performed.

The study subjects will undergo treatments with UltraShape Power device utilizing the U-Sculpt Power Transducer.

During the follow-up period visit will be conducted as follow: 4 weeks (4wk FU), 8 weeks (8wk FU) and 12 weeks (12wk FU) post last treatment (Tx.3). Subject’s fat thickness will be measured in two different methods (Caliper & Ultrasound) and fat reduction will be assessed at each post baseline visit. Circumference will be measured in 3 measurements heights and circumference reduction will be assessed at each post baseline visit. Additionally, investigator and subject questionnaires will be completed. Finally, photography will be performed under visible light conditions of the front, right, left and back view. Most of the assessments will occur at each of the visits to the clinic.

SUTDY OBJECTIVE

The objective of this trial is to evaluate the safety and efficacy of the UltraShape Power device utilizing the U-Sculpt Power Transducer for abdominal non-invasive fat and circumference reduction

Primary Objective

Statistically significant abdominal fat reduction as measured by Ultrasound device post UltraShape Power treatments at 12 weeks follow-up (12wk FU) versus baseline.

 Syneron Medical Ltd. Confidential	Clinical Study to Evaluate the Safety and Efficacy of the UltraShape Power Device Using the U-Sculpt Power Transducer for Abdominal Fat and Circumference Reduction			
	Protocol #	DHF21621	Rev. Date	April 05, 2016

Primary Safety Objective

1. Evaluate the safety of the treatment with the UltraShape Power device utilizing the U-Sculpt Power Transducer during all study.
2. Comfort level during treatment:
Comfort assessment will be performed independently by the subject himself using NSR scale; the subjects will answer this questionnaire after each treatment (Tx.1, Tx.2 and Tx.3).

Secondary Objectives

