1. Statistically significant abdominal fat reduction post UltraShape Power treatments as measured by Ultrasound device at Pre Tx.3, 4 weeks, and 8 weeks follow-up (4wk FU and 8wk FU) versus baseline.
2. Statistically significant abdominal fat reduction post UltraShape Power treatments as measured by calibrated Caliper at Pre Tx.2, Pre Tx.3, 4 weeks, 8 weeks and 12 weeks follow-up (4wk FU, 8wk FU and 12wk FU) versus baseline.
3. Statistically significant abdominal circumference reduction post UltraShape Power treatment/s at Pre Tx.2, Pre Tx.3, 4 weeks, 8 weeks and 12 weeks follow-up (4wk FU, 8wk FU and 12wk FU) versus baseline.
4. Investigator satisfaction:
Satisfaction assessment will be performed by the study investigator using a pre-defined scale questionnaire. The investigator will answer this questionnaire at each follow-up visit (4wk FU, 8wk FU and 12wk FU).
5. Subject improvement and satisfaction:
Improvement and satisfaction assessment will be performed independently by the subject himself using a pre-defined scale questionnaire. The subjects will answer this questionnaire at each follow-up visit (4wk FU, 8wk FU and 12wk FU).

Primary and Secondary Efficacy Endpoint

Primary and secondary objectives will be measured using the next efficacy endpoints:

1. Fat thickness measurements using Ultrasound device
2. Fat thickness measurements using calibrated Caliper
3. Circumference measurements of the abdominal area using Measuring Tape
4. Investigator satisfaction using a pre-defined scale
5. Subject improvement and satisfaction using a pre-defined scale
6. Photography

 Syneron Medical Ltd. Confidential	Clinical Study to Evaluate the Safety and Efficacy of the UltraShape Power Device Using the U-Sculpt Power Transducer for Abdominal Fat and Circumference Reduction			
	Protocol #	DHF21621	Rev. Date	April 05, 2016

Primary Safety Endpoint

The number, severity and type of any adverse event recorded throughout the study and post treatment (discomfort (pain), immediate and delayed response).

1. Occurrence of expected post treatment immediate response including erythema and edema and during all study period based on predefined scale (Table 4).
2. Number, severity and type of any adverse event recorded throughout the course of the study.

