3. Discomfort (pain) level using a 10-point visual analog scale will also be recorded after each benign pigmented lesion clearance treatment– by Numerical Scale Response (NSR), according to Appendix IIIAppendix III - Pain assessment.

STUDY POPULATION

Number of Subjects

This study will be comprised of up to 120 subjects in up to ten (10) investigational sites. Subjects who meet all the inclusion and none of the exclusion criteria will be enroll.

Subject Withdrawal and Replacement

Subjects enrolled in the study can discontinue their participation at any time for any reason without prejudice or reduction in the quality of their medical care. The investigators or sponsor can terminate a subject's participation in this study to protect the subject's health or if the subject fails to follow directions resulting in noncompliance to study procedures. Subjects who withdraw or are terminated from the study may be replaced to ensure at least 120 subjects have completed the study. Subjects who fail to complete the treatment will be replaced and will not be evaluable.

Inclusion Criteria

A subject is eligible to participate in the study if he/she meets all the following inclusion criteria:

1. Signed informed consent to participate in the study.
2. Female and male subjects, ≥ 18 and ≤ 60 years of age at the time of enrolment
3. Fitzpatrick Skin Type I to VI.
4. Abdominal fat thickness of at least 1.5 cm (measured by calibrated caliper).
5. BMI interval: $22 \leq \text{BMI} \leq 30$ (normal to overweight, but not obese).
6. If female, not pregnant, lactating and must be either post-menopausal, surgically sterilized, or using a medically acceptable form of birth control at least 3 months prior to enrollment (i.e., oral contraceptives, contraceptive implant, barrier methods with spermicide or abstinence).

 Syneron Medical Ltd. Confidential	Clinical Study to Evaluate the Safety and Efficacy of the UltraShape Power Device Using the U-Sculpt Power Transducer for Abdominal Fat and Circumference Reduction			
	Protocol #	DHF21621	Rev. Date	April 05, 2016

7. In addition, negative urine pregnancy test as tested before each treatment and at the last visit for women with bearing potential (e.g. not menopause).
8. General good health confirmed by medical history and skin examination of the treated area.
9. Willing to follow the treatment and follow-up schedule and post-treatment care instructions.

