15. Childbirth within the last 12 months or breastfeeding women. Any acute or chronic condition which, in the opinion of the investigator, could interfere with the conduct of the study
16. Unstable weight within the last 6 months (i.e., \pm 3% weight change in the prior six months)
17. Inability to comply with circumference measurement procedure (e.g., inability to hold breath for the required duration).
18. Abdominal fat thickness lower than 2.5 cm after strapping.
19. Participation in another clinical study involving same anatomical areas within the last 6 months (or 30 days in case different anatomical areas were treated in previous trial/s).
20. As per the Investigator's discretion, any physical or mental condition which might make it unsafe for the subject to participate in this study.

STUDY PROCEDURES

Enrollment and Screening

During the first visit, the research staff will screen the subject for eligibility to participate. The inclusion/exclusion criteria will be reviewed, the subject's medical history, an examination of the subject's skin in the treatment areas will be conducted.

The subject will review the informed consent form and the study will be explained to the subject including all risks, potential benefits, procedures, visit requirements, and other alternative treatment options. If the subject qualifies and wishes to participate they will complete the ICF with a signature and date. The original will be retained with subject's records and a copy will be provided to the subject.

The following measurements will be performed and recorded at the specified times throughout the study.

Table 2 – Clinical Evaluation Measurements and Tools

Measurement	When to conduct	Method
Height	Baseline	Scale
Weight	Prior to all treatments (Tx.1, Tx.2 & Tx.3), and at all follow-ups visits (4wk FU, 8wk FU & 12wk FU)	Scale
BMI		Calculation
Fat thickness UltraSound measurement	Baseline, Prior to Tx.3, and at all follow-ups visits (4wk FU, 8wk FU & 12wk FU)	Ultrasound device.
Fat thickness Caliper measurement	Prior to all treatments (Tx.1, Tx.2 & Tx.3), and at all follow-ups visits (4wk FU, 8wk FU & 12wk FU).	Caliper
Circumference measurements		Standardized circumference measuring tape
Photographs		Standardized digital photographs
Urine pregnancy test	Prior to all treatments (Tx.1, Tx.2 & Tx.3), and at the last follow-up visit (12wk FU)	Urine pregnancy test

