Treatment-associated pain	Immediately after each treatment (Tx.1, Tx.2 & Tx.3)	Subject will be asked to rank/ assess pain level during treatment based on the Numerical Scale Response (NSR scale) - Appendix III Appendix III - Pain assessment
Immediate response assessment	Immediately after each treatment (Tx.1, Tx.2 & Tx.3)	Post Treatment Side Effect Severity Scale (Table 4)
Investigator satisfaction	At all follow-up visits (4wk FU, 8wk FU and 12wk FU)	Satisfaction Questionnaire (Table 6)
Subject satisfaction		Satisfaction Questionnaire (Table 6)
Improvement assessment		Improvement Questionnaire (Table 5)
Safety	During treatment and throughout study.	Examination of skin in the treated area, interview subjects, Adverse Events form, Occurrence and Severity Ratings, as well as relation to treatment, action taken and outcome

[figure not shown]

Figure 2: Study Flow-Chart (Visits at the Clinic)

SYNERON CANDELA Syneron Medical Ltd. Confidential	Clinical Study to Evaluate the Safety and Efficacy of the UltraShape Power Device Using the U-Sculpt Power Transducer for Abdominal Fat and Circumference Reduction			
	Protocol #	DHF21621	Rev. Date	April 05, 2016

Pre-Treatment Procedures

Screening and Baseline procedures may be conducted on the same visit day as the treatment, prior to the treatment. It is expected that the screening and baseline procedures will be conducted during the same visit and the treatment visit procedures will take up to 2 hours.

Screening

1. ICF - Prior to any study procedures, informed consent will be obtained. When the subject fully understands the possible benefits and risks of the study, the subject will be asked to sign and date the informed consent form (ICF). The subject will be given a copy of the signed ICF.
2. Subject ID - subjects will be assigned a study subject ID number.
3. Medical History - A medical history will be obtained to determine if the subject meets the study criteria, including a list of all prescribed and over the counter medications taken within the previous 6 months will be recorded.
4. Skin Exam - The subject will undergo a routine skin exam to determine if they meet the study criteria including the presence of fatty tissue deposits in the treatment area.
5. BMI – the volunteers’ height and weight will be taken for calculation of BMI.

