6. Pregnancy Screen - Subjects who are capable of becoming pregnant will undergo a urine pregnancy test. This will be repeated at visits 2 and 3 (prior to all treatments) and at the end of the study (last FU visit/ 12wk FU). If the Screening and Treatment procedures are not conducted on the same day, the urine pregnancy test will be repeated on the treatment day.
7. Scheduling: Subjects will be scheduled to return for the baseline and treatments visit within 14 days following the screening visit. It is preferable the baseline procedures and Tx.1 will be conducted immediately after the Screening visit.

Baseline

1. Photography – Baseline photographs will be obtained using a consistent camera and subject placement settings with a digital imaging system.
2. BMI – the subject weight and height will be taken if baseline visit is a different day than the screening visit.

SYNERON CANDELA Syneron Medical Ltd. Confidential	Clinical Study to Evaluate the Safety and Efficacy of the UltraShape Power Device Using the U-Sculpt Power Transducer for Abdominal Fat and Circumference Reduction			
	Protocol #	DHF21621	Rev. Date	April 05, 2016

Measurements

Measure the Fat Thickness at the Treated Area – Calibrated Caliper

The procedure can be performed only in areas where the fat thickness is ≥ 1.5 cm as measured by a skin fold caliper (or ≥ 3.0 cm as measured by a pinch test), and ≥ 2.5 cm as measured by a skin fold caliper after strapping.

Marking Area for Treatment and Sequence of Treatments

The mark of area to be treated should be copied to a transparent template (at size of A3 paper) to ensure consistent marking of the same area for same patient during the subsequent visits. During copying the treatment area to the transparent template, the following signs will be marked on transparency (Figure 3)

- Margins of area to be treated (A in Figure 3)
- Subject's identification code (B in Figure 3)
- Location of navel (C in Figure 3)
- Sides of right and left (D in Figure 3)

At the subsequent treatment sessions, this transparent template will be placed according to these signs on the abdomen, and the line of treatment area will be re-marked.

[figure not shown]

Figure 3: Marked area of treatment is copied to transparent template, which includes: (A) margin of area to be treated (B) Subject's code (C) location of navel (blue central circle) (D) right and left side. The left picture demonstrates the procedure on patient.

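### The caliper reading that must reach 1.5 cm for entry appears also to be the baseline of the caliper secondary objective, which biases the mean caliper change towards a reduction by an unknown amount

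*Combined protocol and SAP*

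**What the plan says.** **Entry.** Inclusion Criteria item 4 asks for "Abdominal fat thickness of at least 1.5 cm (measured by calibrated caliper". The calibrated-caliper paragraph under Measurements, which follows the Baseline steps, repeats the limit: "The procedure can be performed only in areas where the fat thickness is ≥ 1.5 cm as measured by a skin fold caliper". That sentence then adds a second route, "or ≥ 3.0 cm as measured by a pinch test", which item 4 does not mention. Exclusion Criteria item 18 sets a separate limit on a different reading: "Abdominal fat thickness lower than 2.5 cm after strapping".

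**Endpoint.** Secondary objective 2 seeks a statistically significant fat reduction "as measured by calibrated Caliper at Pre Tx.2, Pre Tx.3, 4 weeks, 8 weeks and 12 weeks follow-up", each against baseline. No minimum reduction is set. The primary objective uses another instrument: "Statistically significant abdominal fat reduction as measured by Ultrasound device".

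**Timing.** Table 2 schedules caliper readings before each treatment and at each follow-up. The numbered Screening list has no caliper item. Pre-Treatment Procedures says "It is expected that the screening and baseline procedures will be conducted during the same visit", although the baseline visit may come up to 14 days after screening. Table 3 puts screening, baseline and Tx.1 in one column. It has two caliper rows, both labelled as taken before strapping; the second is marked only at the three treatment visits.

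**Design.** The study has one arm and each subject's baseline is the only comparator. No replicate caliper readings and no adjustment for regression to the mean are described.

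**The concern.** A lower limit applied to a reading that contains error favours positive errors. Someone whose true thickness is near or below 1.5 cm gets in if the reading happens to be high and is turned away if it happens to be low. Among those admitted, the average error at that reading is therefore above zero. If the same reading is the baseline, later readings without such a limit average lower even when nothing has changed.

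A concurrent control arm selected in the same way would show the same fall, and the comparison would cancel it. Here nothing does. The objective is met by statistical significance alone, so a shift of a fraction of a millimetre can count as success. The caliper is also the only second measure of fat thickness beside the ultrasound result, so a reader may give agreement between the two more weight than it deserves.

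**Working it through.** The plan gives no sample-size, effect-size or variance figure for the caliper, so there is no stated figure to reproduce. The check has two parts.

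**1. Is it the same reading?** Table 2 and the Screening list together leave one pre-strapping caliper reading before Tx.1. This holds even if screening and baseline fall on different days, because no caliper reading is listed at screening. The second caliper row in Table 3 is probably the after-strapping check: it appears only at treatment visits, and an after-strapping limit exists. Its label says otherwise, so this is an inference.

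**2. How large could the effect be?**

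From the documents: limit 1.5 cm; up to 120 subjects (n = 120 used); two-sided alpha 0.05. The synopsis names a Wilcoxon signed rank and/or paired t-test for circumference and subject data, and no test for the caliper; a paired t-test is assumed.

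Assumed: true thickness among volunteers is normal with SD 0.6 cm and mean m of 2.0, 2.5 or 3.0 cm; independent reading-error SD s of 0.15 to 0.3 cm; no device effect; no true within-person change.

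Formulas:
- SD of single readings: S = √(0.6² + s²)
- Standardised limit: z = (1.5 − m)/S; proportion screened out = Φ(z)
- Spurious mean fall: B = (s²/S) × φ(z)/(1 − Φ(z))
- SD of change: √2 × s; noncentrality = B/(√2 × s/√120). The chance of a significant reduction is the upper tail of the noncentral t on 119 degrees of freedom beyond 1.980.

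Example, m = 2.0 and s = 0.3:
- S = √(0.36 + 0.09) = 0.671; z = −0.5/0.671 = −0.745
- φ(z) = 0.302; 1 − Φ(z) = 0.772; ratio 0.391
- B = (0.09/0.671) × 0.391 = 0.0525 cm = 0.53 mm
- SD of change = 4.24 mm; standard error = 4.24/√120 = 0.387 mm
- Noncentrality = 0.525/0.387 = 1.36; chance of a significant reduction 27%

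| Volunteer mean | Screened out | Spurious mean fall | Significant reduction at one visit (nominal 2.5%) |
|---|---|---|---|
| 2.0 cm | 21–23% | 0.13–0.53 mm | 10–27% |
| 2.5 cm | 5–7% | 0.04–0.19 mm | 4–7% |
| 3.0 cm | about 1% | 0.01–0.04 mm | about 3% |

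Using the exact variance after selection moves these rates by about one percentage point at most. A separate set of assumptions (total SD 0.6–0.8 cm, test-retest reliability 0.80–0.95) gives the same pattern: 9–35% at a mean of 2.0 cm, 4–11% at 2.5 cm and 3–4% at 3.0 cm.

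**Conditions that shrink it**, at a mean of 2.0 cm:
- A true within-person change with SD 0.3 cm makes the SD of change √(2s² + 0.3²), and 10–27% becomes 6–19%.
- If the limit is re-applied before Tx.2 and Tx.3 and those who fail it are dropped, the simulated bias is about zero at those two visits. At 12 weeks it is 0.06–0.27 mm, with a rate of 5–10%.

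**The case against.** The strongest reply is that no passage says the qualifying reading is the baseline. Read literally, Table 3 schedules two pre-strapping readings at the first visit, and a split visit could produce a separate qualifying one. That is fair, and is why the point says *appears*. But nothing in the plan assigns one reading to eligibility and another to baseline.

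Second, the 1.5 cm limit may not act as modelled. Subjects who enter by the pinch test are not selected on the caliper. The Treatment Procedure section restricts each procedure to patients then eligible, without saying whether the caliper limit is checked again, and those who do not complete treatment are not evaluable. Both points stand, and both would reduce the bias.

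Third, the size is assumed, and the higher figures need about one volunteer in five to fail the limit. This also stands.

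Three stronger readings are tempting but not supported:
- *Enrolled subjects with readings just above 1.5 cm will fall back.* Under this same model, those with observed readings of 1.5–1.7 cm rise on average, by 0.2–1.8 mm at means of 2.0–2.5 cm. The fall is in the group mean. It arises because people whose true thickness is near or below the limit enter on positive errors.
- *The primary result is biased too.* The primary endpoint is ultrasound, which carries no entry limit. It is exposed only so far as its baseline error correlates with the caliper's, and the documents say nothing on that.
- *Operators will round borderline readings up to 1.5 cm.* This is possible, but the documents offer no evidence of it.

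**Conclusion.** The point holds as a bias of known direction and unknown size in one secondary endpoint. It rests on the inference that a single pre-strapping reading serves both entry and baseline, which is the most plausible reading of Table 2, the Screening list and Table 3 together. Under the stated assumptions it could matter for a significance claim if many volunteers lie near 1.5 cm, and it is negligible if most lie well above. The documents do not show which case applies, so it would be wrong to conclude that a caliper reduction in this trial is mainly artefact. The change is worth considering because it costs little; the validity of the primary analysis does not depend on it.

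**What to change.** At the baseline visit, take two caliper readings before strapping, releasing and repositioning the caliper between them. Use the first only for eligibility. Record the second as the baseline for secondary objective 2 whatever its value, and do not replace it if it is below 1.5 cm. With independent errors the expected null fall is then zero. Error common to both readings on the day leaves a matching share of the bias: if half the error variance is shared, about half remains (0.5 × 0.53 = about 0.26 mm in the worked example). The caliper result should therefore be reported as supportive.

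In the text, say which reading is the caliper baseline and correct or confirm the label of the second caliper row in Table 3. Inclusion Criteria item 4, the caliper paragraph under Measurements and the Treatment Procedure section must be reconciled on two points: whether the pinch test is an alternative route to entry, and whether the caliper limit is applied again before Tx.2 and Tx.3.

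The cost is about one minute and one CRF field per subject and a few sentences of text. The reported caliper reduction may be slightly smaller.

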10. Willingness to refrain from a change in diet/ exercise/medication regimen for the entire course of the study.
11. Willing to have photographs and images taken of the treated areas to be used de-identified in evaluations, publications and presentations.

Exclusion Criteria

A subject is not eligible for participation in this study if he/she meets any of the following exclusion criteria:

1. History of hypertension, ischemic heart disease, valvular heart disease, congestive heart failure, pacemaker/defibrillator, abdominal aortic aneurism
2. Current hyperlipidemia, diabetes mellitus, hepatitis, liver disease, HIV positive status, blood coagulopathy or excessive bleeding, autoimmune or connective tissue disease
3. Having or undergoing any form of treatment for active cancer, or having a history of skin cancer or any other cancer in the areas to be treated, including presence of malignant or pre-malignant pigmented lesions
4. Having any active electrical implant anywhere in the body, such as a pacemaker or an internal defibrillator
5. Having a permanent implant in the treated area, such as metal plates or an injected chemical substance such as silicone
6. Having undergone any other surgery in the treated areas within 12 months of treatment or during the study, including liposuction
7. Previous body contouring procedures in the treatment area within 12 months
8. History of skin disease in the treatment area, known tendency to form keloids or poor wound healing
9. Suffering from significant skin conditions in the treated areas or inflammatory skin conditions, including, but not limited to, open lacerations or abrasions and active cold sores or herpes sores prior to treatment (duration of resolution as per the Investigator's discretion) or during the treatment course
10. Skin lesions in the treatment area other than simple nevi on physical examination (e.g., atypical nevus, tattoo, abrasions) including depressed scars in the treatment area

 Syneron Medical Ltd. Confidential	Clinical Study to Evaluate the Safety and Efficacy of the UltraShape Power Device Using the U-Sculpt Power Transducer for Abdominal Fat and Circumference Reduction			
	Protocol #	DHF21621	Rev. Date	April 05, 2016

11. Very poor skin quality (i.e., severe laxity)
12. Abdominal wall diastasis or hernia on physical examination
13. Abnormal kidney, liver or coagulation functions, abnormal lipid profile or blood count within the last 3 months
14. Obesity (BMI > 30)

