Perform the UltraShape Power utilizing the U-Sculpt Power Transducer treatment according to the instruction in the User Manual.

Expected post treatment side effects are limited to Erythema (blanchable/non-blanchable), Edema, Heat sensation and pain sensation.

Post Treatment Procedures

1. Pain assessment – immediately after each treatment the subjects will be asked to rank the pain sensation during treatment using Numerical Scale Response (NSR; see Appendix III) for the UltraShape Power procedure
2. Safety aspect will be assessed before and after each treatment:
 - a. Clinical effects - All visible and palpable immediate response will be recorded for the entire treatment area using a 4-point severity scale (Table 4)
 - b. Adverse Events – Record the number, severity and type of any adverse event occurred before, through and after treatments.

Return Visits

All subjects will be requested to return to the clinic at the following time-points during the study in order to assess the clinical performance of the device:

- Visit 4: FU1 – 4 weeks (± 7 days) post last treatment.
- Visit 5: FU2 – 8 weeks (± 7 days) post last treatment.
- Visit 6: FU3 – 12 weeks (± 7 days) post last treatment.

At each return visit the following procedures will be conducted and data recorded:

- Weight.
- Ultrasound fat-thickness measurements.
- Caliper fat-thickness measurements.
- Circumference measurements.

SYNERON CANDELA Syneron Medical Ltd. Confidential	Clinical Study to Evaluate the Safety and Efficacy of the UltraShape Power Device Using the U-Sculpt Power Transducer for Abdominal Fat and Circumference Reduction			
	Protocol #	DHF21621	Rev. Date	April 05, 2016

- Skin assessment for clinical effects due the procedures:
 - Post treatment response and adverse events.
- Photographs as conducted at baseline.
- Satisfaction questionnaire performed by the investigator using the Global Aesthetic Improvement (GAI).
- Completion of the Subject Follow Up questionnaire:
 - Subjective Improvement and satisfaction performed by the subject using the Global Aesthetic Improvement (GAI).
- At the final visit a urine pregnancy test will be performed for women with bearing potential.

DATA ANALYSIS

Recording

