All data will be recorded on site source documents and transcribed onto Case Report Forms (CRFs). The site will be monitored by Syneron staff or designees to assure adherence to the clinical trial requirements, subject safety, protocol procedures, and for data accuracy. The Case Report Forms and images will be reviewed and retrieved during the monitoring visit. All source documentation will remain in the subject's files at the site.

Review and Analysis of all data collected will be conducted by the Sponsor or designee as described for this protocol with the following data:

Demography and Baseline Measurements

Demographic and baseline/screening measurements (e.g., weight, height and digital images) will be collected and descriptively presented.

Treatment Visit

Skin assessment by the PI, photographs of the treated region, and pain scores will be collected used to document any adverse events to assess the device performance.

Follow-up Visit Measurements

Follow-up measurements for weight, circumference and digital images will be used for comparative measurements with their respective measurement at baseline. Primary endpoints will be evaluated 12 weeks post last treatment (Tx.3). Secondary endpoints may be evaluated at all visits.

 Syneron Medical Ltd. Confidential	Clinical Study to Evaluate the Safety and Efficacy of the UltraShape Power Device Using the U-Sculpt Power Transducer for Abdominal Fat and Circumference Reduction			
	Protocol #	DHF21621	Rev. Date	April 05, 2016

Safety

Safety of device procedure will be evaluated through skin assessments by the PI and research staff. The occurrence and severity of all complications from the start of the study will be recorded.

Protocol Revisions and/or Deviations

With the exception of emergency situations, no changes or deviations in the conduct of this protocol will be permitted without the prior approval of the sponsor.

The IRB/IEC that granted original approval for the study must be notified of all changes in the protocol, and will approve any change or deviation that may increase risk to the subject, and/or that may adversely affect the rights of the subject or validity of the investigation.

In the event of an emergency, the Investigator will institute any medical procedures deemed appropriate. However, all such procedures must be promptly reported to the sponsor and the IRB/IEC.

ADVERSE EVENTS (AE)

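### Inclusion 10 and exclusion 16 admit a recently started weight-loss regimen, and the weights collected at each visit have no pre-specified role in the fat-thickness analysis

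*Combined protocol and SAP*

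**What the plan says.** Protocol, Inclusion Criteria, item 10 requires "Willingness to refrain from a change in diet/ exercise/medication regimen for the entire course of the study". Exclusion Criteria, item 16 bars "Unstable weight within the last 6 months", defined by a "3% weight change in the prior six months" in either direction. No exclusion item names a current weight-loss regimen or a drug taken to reduce weight.

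Under Screening, item 3 (Medical History), "a list of all prescribed and over the counter medications taken within the previous 6 months will be recorded". This is the only scheduled medication record.

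Under Return Visits, the list introduced by "At each return visit the following procedures will be conducted and data recorded" includes weight, ultrasound, caliper and circumference, but nothing on diet, exercise or medication. Table 2 and Table 3 have no such item either. Table 2 does schedule weight "Prior to all treatments (Tx.1, Tx.2 & Tx.3), and at all follow-ups visits (4wk FU, 8wk FU & 12wk FU").

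Under Follow-up Visit Measurements, "Follow-up measurements for weight, circumference and digital images will be used for comparative measurements with their respective measurement at baseline". No rule links weight change to the ultrasound, caliper or circumference results.

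The Study Design Overview describes one arm with baseline as the control. The Primary Objective is a statistically significant ultrasound fat reduction at 12 weeks after the last treatment compared with baseline.

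**The concern.** The regimen criterion looks forward from entry and the weight criterion looks backward from it. A subject who began a calorie-restricted diet, an exercise programme or a weight-reducing drug shortly before baseline meets item 10 by continuing it, and passes item 16 if the loss so far is under 3%. The continuing loss then falls inside the 16-week observation period.

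With no concurrent control, that loss cannot be separated from a device effect by design, and any significant fall from baseline satisfies the primary objective. The volunteers are people seeking abdominal fat reduction, so concurrent efforts to lose weight are plausible. The error runs in the device's favour. The weights that could qualify the result are collected, but the plan does not say how they bear on fat thickness.

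**Working it through.** The documents give no effect size, SD or power, so there is no figure to reproduce. What follows is an illustration. Document inputs are n = 120 (the stated maximum), BMI 22 to 30, the 3% limit, 16 weeks on study and two-sided alpha 0.05. The Statistical Methods sentence names circumference and subject assessments, so applying that alpha to ultrasound is an assumption.

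**1. How much loss passes exclusion 16.** Weight = BMI × height². Heights of 1.60 to 1.80 m and losses of 0.25 to 0.5 kg per week are assumed.
- Lightest: 22 × 1.60² = 56.3 kg, and 3% is 1.69 kg. At 0.5 kg per week that takes 1.69 / 0.5 = 3.4 weeks.
- Heaviest: 30 × 1.80² = 97.2 kg, and 3% is 2.92 kg. At 0.25 kg per week that takes 2.92 / 0.25 = 11.7 weeks.

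A subject could therefore be about 3 to 12 weeks into a regimen and still qualify. Continuing at the same rate for 16 weeks removes between 16 × 0.25 / 97.2 = 4.1% and 16 × 0.5 / 56.3 = 14.2% of body weight without breaching item 10.

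**2. Effect on mean ultrasound thickness.** Assumed: 80 kg subject with 22 kg of fat, 75% of lost weight is fat, 25 mm abdominal thickness scaling with fat mass, and 20% of subjects affected.
- 1 kg lost: 0.75 / 22 × 25 = 0.85 mm each; × 0.20 = 0.17 mm in the study mean.
- 4 kg lost: 3 / 22 × 25 = 3.4 mm each; × 0.20 = 0.68 mm in the study mean.

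**3. Mean change that is just significant.** 1.98 × SD / √120, with an assumed SD of change of 3 to 5 mm.
- SD 3 mm: 0.54 mm.
- SD 5 mm: 0.90 mm.

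Each kilogram lost moves the study mean by 0.17 mm. At SD 3 mm the loss must exceed 0.54 / 0.17, about 3.2 kg, to reach the threshold alone. At SD 5 mm it must exceed 0.90 / 0.17, about 5.3 kg, which is outside the 1 to 4 kg range.

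**4. Chance of a significant reduction with an inactive device.** A fraction f of subjects has a mean regimen-driven fall of s within-subject SDs. The study mean is f × s, the SD is √(1 + f(1 − f)s²), and power is taken from the noncentral t at n = 120. The nominal rate in that direction is 2.5%.

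| Fall in affected subjects | f = 10% | f = 20% | f = 30% |
|---|---|---|---|
| 0.5 SD | 8% | 19% | 36% |
| 1 SD | 18% | 52% | 84% |
| 2 SD | 46% | 92% | 99.8% |

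The assumptions in steps 2 and 3 correspond to falls between 0.85 / 5 = 0.17 SD and 3.4 / 3 = 1.1 SD, so the 2 SD row lies beyond them.

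**The case against.** The strongest reply is that the plan is not blind to weight. Exclusion 16 removes anyone whose regimen has already moved weight by 3% in six months. Weight is taken at all six treatment and follow-up visits and is to be compared with baseline. The medication history is taken to judge eligibility, and a subject can be terminated "if the subject fails to follow directions resulting in noncompliance to study procedures".

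Much of this stands. A reader might infer that any subject on a weight-loss regimen qualifies, that nothing is rechecked after entry, or that affected subjects could never be identified. The documents support none of these. Only recent regimens, or those with little effect so far, pass. The main consequence of a regimen, body weight, is rechecked at every visit. A loss of a few kilograms would show in planned data.

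What remains is narrower. Exclusion 16 cannot catch a regimen that is about to work, and the protocol names no source for the weight six months earlier. The medication list has no criterion acting on weight-reducing drugs and is not updated. The termination power has no regimen trigger and no scheduled data to invoke it. Adverse event recording covers reactions to other medications only when judged device-related. Weight alone cannot show whether or when a regimen changed, and it can miss exercise-driven fat loss offset by lean mass.

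It is also fair that every input to the size is assumed and that most of the 0.17 to 0.68 mm range falls below the significance threshold. A spurious positive result is not the typical outcome on those figures.

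**Conclusion.** The point holds in this form: a recently started weight-loss regimen with under 3% lost so far is admissible, adherence to the regimen is not asked about after screening, and the visit weights have no pre-specified role in the fat-thickness analysis. Fat lost through such a regimen counts towards the primary objective and always biases in the device's favour.

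The size is uncertain. With 20% of subjects affected and losses of 1 to 4 kg, the bias reaches significance alone only when the SD is near 3 mm and the loss exceeds about 3.2 kg. Below that it still adds to any true effect and raises the false-positive chance, for example to 19% with 20% of subjects shifted by 0.5 SD. The prevalence, body composition, proportional thinning, SD, heights and loss rates are all assumptions. This is an inexpensive improvement that should be made. It is not evidence that the study must give a false result.

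**What to change.** 1. Reword inclusion 10 so that diet, exercise and any medication taken to reduce weight have been unchanged over the six months already used in exclusion 16, and the subject is not on an active weight-loss regimen at baseline. Limiting the medication clause to drugs taken for weight reduction avoids a conflict with the three-month contraception minimum in inclusion 6.
2. At Tx.2, Tx.3 and each follow-up, update the medication list and record yes or no, with date, for a change in diet or exercise.
3. Pre-specify three sensitivity analyses of the 12-week ultrasound change, each shown beside the all-subjects result:
   - mean change adjusted to zero weight change;
   - restriction to subjects within 3% of baseline weight;
   - omission of subjects with a recorded regimen change.

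The third analysis is not enough alone, because a subject who continues a diet begun before entry reports no change and stays in. The restricted analysis also leaves some bias: 3% of 80 kg is 2.4 kg, and 2.4 × 0.75 / 22 × 25 = 2.0 mm on the assumptions above. The weight-adjusted analysis is therefore needed as well. All three condition on post-baseline information, so they support the all-subjects analysis and do not replace it.

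Cost: slightly slower recruitment because recent dieters are screened out, a short CRF page at visits already planned, and a few extra tables. The reworded criterion still rests on self-report.
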